12.0 SAFETY ANALYSES

All analyses will be conducted by Analysis Period (s) over time at each analysis visit or overall in the Safety Analysis Set. Please see definition for Analysis Period and Analysis Visit in [Section 20.1](#) and [20.2](#) respectively.

The following variables will be evaluated to assess the safety and tolerability of RBP-6000:

- Incidence of treatment-emergent adverse events (TEAEs).
- Changes in clinical laboratory results.
- Vital sign measurements.

Other Safety Variables are:

- Medical history.
- Urine pregnancy test.
- Suicidality using the C-SSRS.
- Prior and concomitant medications.
- Local injection site tolerability (e.g., injection site grading).
- Injection site pain using a subject-reported VAS.
- Weight, BMI, waist circumference, hip circumference and waist-to-hip ratio.
- Behavioral therapy.

12.1 ADVERSE EVENTS

12.1.1 Adverse Events

Imputation rules for AE (for determination of TEAE only) start date are in Section 20.7.

Treatment-emergent Adverse Events (TEAEs)

TEAEs are those that started following the first dose of RBP-6000 and before the Treatment End Date (the maximum of the date of the end-of-study/ Early Termination (EOS/ET) visit and the date of last injection + 28 days) in this study, or were present prior to the first dose of RBP-6000 regardless of causality and increased in severity within the treatment period (defined in section 20.1) AEs include those events that are ongoing at the time a subject rolls-over from the RB-US-13-0003.

Treatment-related Adverse Events

A summary of TEAEs will be presented for the Safety Analysis Set, including the number and percentage of subjects reporting at least one TEAE, the number and percentage of subjects with the following:

- Related TEAEs
- SAEs
- Related SAEs
- TEAEs with an outcome of death
- TEAEs
- Severe TEAEs
- TEAEs leading to RBP-6000 discontinuation

A breakdown of the number and percentage of subjects reporting each TEAE categorized by SOC and PT coded per the MedDRA dictionary version 19.0 will be presented in the Safety Analysis Set. Note that counting will be by subject not by event and subjects will be only counted once within each SOC or PT.

A further tabulation of events experienced by $\geq 5\%$ of subjects by SOC and PT will be presented for the Safety Analysis Set. If there are no TEAEs experienced $\geq 5\%$ of subjects by any PT, this table will be empty.

A summary of events reported, categorized by severity, will also be provided. Subjects with multiple events within a SOC or PT will be counted under the category of their most severe event within that SOC or PT. A further tabulation of severe AE/TEAEs will be presented by SOC and PT.

Additionally, treatment-related AEs/TEAEs will be summarized by maximum severity (mild, moderate, or severe). A breakdown of severe treatment-related AEs/TEAEs by SOC and PT will be provided.

All AEs (including non-TEAEs) recorded on the CRF will be listed.

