20.0 DATA HANDLING CONVENTIONS

20.1 REFERENCE DATES AND ANALYSIS PERIODS

There are two analysis periods in this study:

- Treatment Period (TP)
- Safety Follow-Up Period (SFU).

Treatment Period starts from Treatment Start Date and ends at Treatment End Date. Treatment Start Date (or Day 1) for a subject is the date of the first injection. Treatment End Date for a subject is the maximum of the date of the end-of-study/ Early Termination (EOS/ET) visit and the date of last injection + 28.

Safety Follow-Up Period starts from Safety Follow-Up Start Date and ends at Safety Follow-Up End Date, which are defined for all subject who have assessments in the Follow-Up period.

Safety Follow-Up Start Date for a subject is Treatment End Date +1.

Safety Follow-Up End Date for a subject is defined as the date of visit at Week 29 or unscheduled visit after the Treatment End Date (defined as above) for AE/concomitant medication reporting or lab/vital signs assessment, whichever comes later. That is, Follow-up end date is max (Follow-up Start Date, date of visit at Week 29, last unscheduled visit after the Treatment End Date to report AE/concomitant medication or to do lab/vital signs assessment, if available).

Any records collected prior to first injection date/time will be considered as Screening records. And any records collected after the Treatment End Date will be considered as Safety Follow-up records.

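### SAP 12.1.1 ends the window for new-onset TEAEs one day before the Treatment Period ends, and on the nominal schedule the lost day is the end-of-study visit (Day 169)

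*SAP*

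**What the plan says.** The TEAE definition in SAP 12.1.1 has two limbs.

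- **New onset:** "TEAEs are those that started following the first dose of RBP-6000 and before the Treatment End Date".
- **Worsening of a pre-existing event:** the event must have "increased in severity within the treatment period (defined in section 20.1").

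SAP 20.1 sets the periods. The Treatment End Date is the later of the EOS or early-termination (ET) visit date and the last injection date plus 28 days. Then:

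- "Treatment Period starts from Treatment Start Date and ends at Treatment End Date"
- "Safety Follow-Up Start Date for a subject is Treatment End Date +1"
- "any records collected after the Treatment End Date will be considered as Safety Follow-up records"

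On the protocol side, section 9.5.1.1 leaves out of the safety analysis only AEs that began after the EOS visit. Section 6.9.2 puts no upper limit on TEAE onset. SAP 21 declares no change from the protocol analyses.

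SAP 12.1.5 asks for a follow-up table of AEs potentially pertaining to drug withdrawal. Appendix 3 lists it as Table 14.3.1.13 but titles it as a table of treatment-emergent events.

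**The concern.** The two SAP sections disagree about one day. SAP 20.1 puts the Treatment End Date inside the Treatment Period, while the new-onset limb of 12.1.1 stops the day before. The definition is also uneven within itself, because the worsening limb uses the 20.1 period and so includes that day. On the same date a worsened pre-existing event would count and a new event would not. No reason is given.

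The day matters because, on schedule, it is the EOS visit. That visit has the physical examination, the only scheduled post-baseline laboratory tests, vital signs and an AE assessment, so onset dates on that day are plausible. Protocol 6.2 requires a clinically significant change on the EOS examination to be reported as an AE.

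TEAE incidence is the first safety variable in SAP 12.0. The serious, severe, related and special-interest tables in Appendix 3 are titled as TEAE tables, so one flag feeds them all. Relative to *on or before*, the word *before* can only lower counts. For example, an AE for raised ALT found at EOS and dated to the visit would be missing from Table 14.3.1.16 (hepatic disorders).

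Table 14.3.1.13 raises a related problem. A program that requires both the TEAE flag and onset in follow-up would return an empty table, which could be misread as no withdrawal events after treatment.

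**Working it through.** This is date arithmetic applied to the stated rules.

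**Inputs**

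- Injection 6 on Day 141 and EOS on Day 169, window -2/+7 days (Protocol Appendix 1; Protocol 9.3 also gives Day 169).
- Treatment End Date = max(EOS/ET visit date, last injection + 28) (SAP 20.1).
- New-onset TEAE: onset after the first dose and < Treatment End Date (SAP 12.1.1).
- Treatment Period: first injection to Treatment End Date, inclusive (SAP 20.1).
- Follow-up: from Treatment End Date + 1 (SAP 20.1), applied here to onset dates.

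**The plan's own figure.** Injections every 28 days from Day 1 fall on Days 1, 29, 57, 85, 113 and 141. Then 141 + 28 = 169, which is the scheduled EOS day. So the Treatment End Date is max(169, 169) = Day 169.

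**New AE by onset day, on schedule**

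| Onset | In Treatment Period | TEAE as written | Follow-up | TEAE with *on or before* |
|---|---|---|---|---|
| Day 168 | yes | yes | no | yes |
| Day 169 | yes | no (169 < 169 is false) | no | yes |
| Day 170 | no | no | yes | no |

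**Across the EOS window, injection 6 on Day 141.** The window is 169 - 2 = 167 to 169 + 7 = 176, which is 10 dates.

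- EOS on Day 167 or 168 (2 dates): the Treatment End Date is Day 169. An AE dated to the visit is still a TEAE, and the lost day is Day 169, after the visit.
- EOS on Days 169 to 176 (8 dates): the Treatment End Date is the visit date. A new AE dated to the visit is not a TEAE.

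With *on or before*, no day is unassigned or counted twice for any of the 10 dates.

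**Early termination example.** Last injection Day 85, ET visit Day 100: the Treatment End Date is max(100, 85 + 28) = Day 113. An AE on the ET day is a TEAE, and only Day 113 falls in the gap.

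**Table 14.3.1.13.** A new-onset TEAE needs onset < End Date (or ≤ End Date after the edit). Onset in follow-up needs ≥ End Date + 1. No date satisfies both, before or after the edit.

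**Size per affected subject.** SAP 12.1.1 says: "Note that counting will be by subject not by event and subjects will be only counted once within each SOC or PT". A row changes only if the lost event is that subject's only TEAE in the row. At the approximate planned 300 subjects, each such subject lowers the row by 1/300 = 0.33 percentage points.

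**The case against.** The strongest reply is that the intended reading can be recovered. SAP 12.0 says "All analyses will be conducted by Analysis Period (s) over time at each analysis visit or overall in the Safety Analysis Set" and points to 20.1, and most of the TEAE tables in Appendix 3 are titled as covering the Treatment Period. The harm therefore needs someone to code one sentence literally. That is fair and keeps the point minor. But two programmers, one following 12.1.1 and one following 20.1, would produce different flags, and a definition should not allow that.

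Other points, and what stands of each:

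- **Follow-up membership.** SAP 20.1 assigns records by when they are collected. An AE with onset on the Treatment End Date but first reported at the Week 29 contact might be treated as a follow-up record. The statement that such an event belongs to neither group, and the empty-table result, hold when onset date is used. The SAP gives no separate rule for AEs.
- **Worsening events.** Protocol 6.9.5 has severity changes recorded as separate events, so a program might test a worsening record under the new-onset limb. The worsening limb as written covers it, but referring both limbs to 20.1 removes the doubt.
- **Protocol 9.5.1.1.** When EOS is on Day 167 or 168 and the Treatment End Date is Day 169, *on or before* adds a day after EOS, which the protocol sentence excludes. That is true, although the SAP period already runs past EOS in those cases. No claim is made about the net difference from the protocol.
- **The 8 of 10.** This counts dates, not subjects, and fixes injection 6 on Day 141. If injection 6 may fall on Days 139 to 148 and EOS independently on Days 167 to 176, EOS is at least 28 days after injection in 10 + 9 + ... + 1 = 55 of 100 date pairs. The documents do not say whether the EOS window follows the nominal day or the last injection.
- **The ALT example.** The documents do not say whether a laboratory AE takes the sample or the result date. Testing is at a central laboratory, and an AE dated after the Treatment End Date is excluded under either wording. The laboratory values stay in the laboratory tables regardless.

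**Conclusion.** The concern holds at minor severity. As written, SAP 12.1.1 drops new-onset AEs dated on the Treatment End Date from the TEAE tables, against the SAP's own period definition. That date is the EOS/ET visit whenever the visit is 28 or more days after the last injection.

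The gap is one day per subject. AEs reported at EOS with an earlier onset are not affected, nor are AEs dated to an EOS/ET visit less than 28 days after the last injection. The number of events lost cannot be estimated, because the documents give neither AE rates nor a rule for dating onset. It is likely small. Nothing disappears from the report: "All AEs (including non-TEAEs) recorded on the CRF will be listed".

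The conclusion assumes a literal reading of *before* and classification by onset date. The title of Table 14.3.1.13 is wrong in any case, because SAP 12.1.5 specifies AEs without the treatment-emergent restriction.

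**What to change.** 1. In SAP 12.1.1, insert *on or* ahead of *before* in the new-onset limb, so that onset on the Treatment End Date counts. Alternatively, refer both limbs to the Treatment Period of SAP 20.1.
2. Delete *Treatment-emergent* from the title of Table 14.3.1.13 so that it matches SAP 12.1.5. This is needed even after the first edit, because follow-up still starts one day after the last possible new-onset TEAE.

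The cost is two words added to one definition and one word removed from one title, with no new data or tables. Any TEAE flag already programmed must be rerun, and TEAE counts may rise slightly.

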12.1.2 Serious Adverse Events

SAEs and treatment-related SAEs will be summarized separately by SOC and PT for the Safety Analysis Set.

All SAEs recorded on the CRF will be listed for all subjects.

12.1.3 Adverse Events Leading to Discontinuation

A summary of AEs/TEAEs and treatment-related AEs/TEAEs leading to discontinuation (defined as an event with an outcome of 'drug withdrawn' in the CRF) will be provided, grouped by SOC and PT, for the Safety Analysis Set. Supportive listings will be provided.

All AEs leading to discontinuation recorded on the CRF will be listed. Additionally, TEAEs leading to dose reduction will be listed.

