### **6.9 Adverse Events Assessments**

#### **6.9.1 Adverse Event Definition**

In accordance with ICH and United States Food and Drug Administration (FDA) guidance, any untoward medical occurrence incurred by a subject that occurs after the first study-related procedure to the completion of the Safety Follow-Up Visit and is associated with the use of the drug, regardless of the presence of causal relationship, is a reportable AE. AEs that are ongoing at the time of the RB-US-13-0003 EOS visit will be recorded in the eCRF for this study.

All subjects participating in the study that have a EOS/ET Visit will be contacted by telephone for a safety follow-up assessment of AEs (new or ongoing) and use of any concomitant medications.

Abnormal results of diagnostic procedures, including laboratory test abnormalities, are considered AEs if they:

- Result in discontinuation from the study,
- Require treatment or any other therapeutic intervention,
- Require further diagnostic evaluation (excluding a repetition of the same procedure to confirm the abnormality), or
- Are associated with clinical signs or symptoms that would have a significant clinical impact, as determined by the Investigator.

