#### 9.5.1.1 Adverse Events

All AEs will be coded using the most up-to-date version of the Medical Dictionary for Regulatory Activities (MedDRA) and reported to the FDA. AEs that began after the EOS visit will not be included in the safety analysis. Only TEAEs occurring post administration of RBP-6000 will be included in the safety analysis (See [Section 6.9.2](#)).

The incidence of AEs (number and percent of subjects reporting the AE at least once during the study) will be summarized for all AEs, by the relationship to IMP and by severity.

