14.3 Safety Data Tables & Figures

Table 14.3.1.1 Overall Summary of Treatment-Emergent Adverse Events – Safety Analysis Set
Table 14.3.1.2 Summary of Treatment-Emergent Adverse Events by MedDRA System Organ Class and Preferred Term During the Treatment Period – Safety Analysis Set
Table 14.3.1.3 Summary of Treatment-Emergent Adverse Events Experienced by >=5% of Subjects by MedDRA Preferred Term During Treatment Period– Safety Analysis Set

Table 14.3.14 Summary of Treatment-Emergent Adverse Events Leading to Discontinuation by MedDRA System Organ Class and Preferred Term During Treatment Period- Safety Analysis Set

Table 14.3.1.5 Summary of Deaths due to Adverse Event (AE) - Safety Analysis Set

Table 14.3.1.6 Summary of Serious Treatment-Emergent Adverse Events by MedDRA System Organ Class and Preferred Term During Treatment Period- Safety Analysis Set

Table 14.3.1.7 Summary of Serious Treatment-Emergent Adverse Events Related to Study Treatment by MedDRA System Organ Class and Preferred Term During Treatment Period- Safety Analysis Set

Table 14.3.1.8 Summary of Treatment-Emergent Adverse Events by Maximum Severity, MedDRA System Organ Class and Preferred Term During Treatment Period – Safety Analysis Set

Table 14.3.1.9 Summary of Treatment-Emergent Adverse Events Related to Study Treatment by Maximum Severity, MedDRA System Organ Class and Preferred Term During the Treatment Period- Safety Analysis Set

Table 14.3.1.10 Summary of Severe Treatment-Emergent Adverse Events Related to Study Treatment Leading to Discontinuation by MedDRA System Organ Class and Preferred Term During the Treatment Period- Safety Analysis Set

Table 14.3.1.11 Summary of Severe Treatment-Emergent Adverse Events by MedDRA System Organ Class and Preferred Term During the Treatment Period- Safety Analysis Set

Table 14.3.1.12 Summary of Treatment-Emergent Adverse Events Potentially Pertaining to Drug Withdrawal Symptoms by MedDRA System Organ Class and Preferred Term During the Treatment Period- Safety Analysis Set

Table 14.3.1.13 Summary of Treatment-emergent Adverse Events Potentially Pertaining to Drug Withdrawal Symptoms During the Safety Follow-up Period for Subjects Who Entered into the Safety Follow-up Period

Table 14.3.1.14 Summary of Treatment-Emergent Adverse Events Potentially Pertaining to Injection Site Reactions by MedDRA System Organ Class and Preferred Term During the Treatment Period- Safety Analysis Set

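### A carried-over adverse event of unchanged severity that ends RBP-6000 treatment is listed but reaches no discontinuation table

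*SAP*

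**What the plan says.** - **Recording.** Protocol 6.9.1 states that "AEs that are ongoing at the time of the RB-US-13-0003 EOS visit will be recorded in the eCRF for this study". SAP 12.1.1 likewise counts events ongoing at roll-over as adverse events.
- **Treatment-emergence.** Under protocol 6.9.2 a pre-existing event qualifies if either its frequency or its severity rises after treatment starts. SAP 12.1.1 keeps severity alone: it admits events that "were present prior to the first dose of RBP-6000 regardless of causality and increased in severity within the treatment period".
- **Discontinuation text.** SAP 12.1.3 calls for "A summary of AEs/TEAEs and treatment-related AEs/TEAEs leading to discontinuation", by SOC and preferred term. An event qualifies if the CRF records the drug as withdrawn. The same section says that every AE leading to discontinuation will be listed.
- **Discontinuation tables.** SAP Appendix 3 has "Table 14.3.14 Summary of Treatment-Emergent Adverse Events Leading to Discontinuation" (the number is evidently 14.3.1.4) and Table 14.3.1.10, which is confined to severe, related, treatment-emergent events leading to discontinuation.
- **Governing rule.** Protocol 9.5.1.1 says "Only TEAEs occurring post administration of RBP-6000 will be included in the safety analysis" and refers back to 6.9.2.
- **Declared changes.** SAP 21.0 reports none.
- **Serious events.** SAP 12.1.2 says "SAEs and treatment-related SAEs will be summarized separately by SOC and PT for the Safety Analysis Set". The matching titles are "Table 14.3.1.6 Summary of Serious Treatment-Emergent Adverse Events by MedDRA System Organ Class and Preferred Term" and "Table 14.3.1.7 Summary of Serious Treatment-Emergent Adverse Events Related to Study Treatment".

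**The concern.** In most trials the treatment-emergent filter separates events that arose before the drug from those that arose on it. Here Day 1 is not the start of exposure. Protocol 1.1 shows that subjects come from RB-US-13-0003, where they could receive up to 12 injections, or up to 6 if they had entered from RB-US-13-0001. An event ongoing at roll-over may well have begun on RBP-6000. If it persists and eventually makes the subject stop, that is a tolerability outcome of long-term treatment, and the protocol synopsis names discontinuations due to adverse events among the safety assessments. The SAP text appears to cover such a case, but the table titles exclude it. A reader working from the tables alone would not see it.

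**Working it through.** No power, alpha or effect size bears on this, and the plan gives no figure to reproduce. The check sets the rules side by side. I take initiation of treatment to mean the first injection in this study, as the SAP does.

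**Step 1. Follow four kinds of event that lead to withdrawal of the drug.**

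| Event | TEAE under protocol 6.9.2 | TEAE under SAP 12.1.1 | In Table 14.3.1.4 | In Listing 16.2.16 |
|---|---|---|---|---|
| Starts after Day 1 | yes | yes | yes | yes |
| Carried over, severity rises | yes | yes | yes | yes |
| Carried over, more frequent, same severity | yes | no | no | yes |
| Carried over, unchanged | no | no | no | yes |

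All four rows are adverse events of this study, so read literally all four fall under the SAP 12.1.3 text. The last two do not reach the table. The third is left out although the protocol's own TEAE-only rule would include it.

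**Step 2. Look for another table that picks them up.** Tables 14.3.1.1 to 14.3.1.20 are 20 tables. All but one, 20 − 1 = 19, are titled for treatment-emergent events. The exception is 14.3.1.5, deaths due to an adverse event, so a fatal case would show there. A non-fatal one is in no AE table by SOC and preferred term.

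**Step 3. Check the treatment-related half of the sentence.** The only table for related events leading to discontinuation is 14.3.1.10, and it takes severe events only. A mild or moderate related event that stops treatment is in 14.3.1.4 without its relationship and in 14.3.1.9 without its consequence. This gap affects ordinary treatment-emergent events as well as carried-over ones.

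**Step 4. Size.** The documents do not say how many events were carried over. With the planned enrolment of about 300:
- one subject: 1/300 = 0.33 percentage points
- two subjects: 2/300 = 0.67 points
- three subjects: 3/300 = 1.00 point

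Over an assumed range of 0 to 3 subjects, a count of all AEs leading to discontinuation would exceed the tabulated figure by 0 to 1.0 point.

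**The case against.** The best defence is that the tables obey the protocol. Protocol 9.5.1.1 confines the safety analysis to treatment-emergent events. The overall summary in SAP 12.1.1 has a row for TEAEs leading to discontinuation. The combined AE/TEAE form also appears in 12.1.1 for severity and relatedness summaries whose tables are TEAE-only, so it may be shorthand. On that view, narrowing the wording of 12.1.3 is enough.

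Much of this stands. The treatment-emergent count should stay the main figure, and narrower wording would remove the mismatch between text and titles. It would still leave persisting on-drug events out of the tables. It also does not cover events of increased frequency, which the protocol's rule includes. Nor is the shorthand reading certain: SAP 12.1.3 lists AEs leading to discontinuation but TEAEs leading to dose reduction, and the titles of Listings 16.2.16 and 16.2.25 keep that contrast.

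Two stronger inferences are tempting but not supported:
- **That the SAE tables have the same defect.** The SAE wording is ambiguous, because SAP 12.1.1 places its SAE rows inside a summary of TEAEs. Seriousness and severity are distinct in protocol 6.9.5, but its scale ties probable hospitalization to the severe grade and asks for a separate record when severity changes. A carried-over event that turns serious would usually be regraded, recorded anew and so become treatment-emergent. The main case left is an event already severe at roll-over.
- **That the TEAE filter alone would set the discontinuation table against disposition.** The two can differ anyway. Disposition takes one primary reason per subject (protocol 6.12), while SAP 12.1.3 works from the action recorded for each event.

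**Conclusion.** The point holds for the discontinuation tables. A non-fatal adverse event carried over at unchanged severity that ends in withdrawal of the drug is listed but is in no AE table by SOC and preferred term. The SAP also narrows the protocol's definition of treatment-emergence by dropping frequency, without declaring it. And the promised summary of related events leading to discontinuation is planned for severe events only.

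The effect is probably small: 0.33 points per subject if 300 enrol, and possibly no subjects at all. The 0 to 3 range is an assumption. The imputation rules in SAP 20.7 can shrink the gap further, because an incomplete start date may be set to the first-dose date. The study is single-group and descriptive, so no test result is at risk.

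A reader might infer that these events are hidden, or that every TEAE table must be widened. Neither follows. SAP 12.1.1 to 12.1.3 list all such events, and the TEAE restriction in the general incidence tables is what the protocol asks for. The case for acting is that the outcome is a named safety assessment and the correction is cheap.

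**What to change.** 1. **SAP 12.1.1:** restore frequency alongside severity, or declare the narrower rule in SAP 21.0. Protocol 6.9.3 does not list frequency among the attributes documented for each event, so first check that the eCRF can support it. If the narrower rule stays, give carried-over events of increased frequency their own line in the tables below, since the protocol regards them as treatment-emergent.
2. **Table 14.3.1.4:** correct the number and keep the TEAE count. Add a separate row for events carried over from RB-US-13-0003, not treatment-emergent under protocol 6.9.2, that led to withdrawal of the drug in the Treatment Period.
3. **Table 14.3.1.10:** cover all related events leading to discontinuation, whatever their severity, with the same extra row.
4. **SAP 21.0:** record the added rows as an addition to protocol 9.5.1.1, since protocol 9.1 requires departures to be set out in the SAP.

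The same row in Tables 14.3.1.6 and 14.3.1.7 is optional. The other AE tables need no extra row.

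The cost is two amended tables, one definition to settle and one entry in SAP 21.0, using AE records of this study. The downside is slightly more output and possibly a slightly less favourable discontinuation figure. If the new row is zero, that is worth reporting.
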